6.4. Treatment

6.4.1 Objectives

- A. To investigate if change in basic lifestyle measures from baseline to 3 months, and 1 year, respectively, after randomization differ in the two treatment arms.
- B. To investigate if the proportion of patients initiating and adhering to optimal medical treatment (event prevention, antianginal therapy), differ in the two treatment arms 1 year after randomization.

6.4.2 Endpoints

- A. Change in basic lifestyle measures from baseline to 3 months, and 1 year, respectively, after randomization. (Basic lifestyle measures will be assessed by the HeartDiet questionnaire).
- B. Difference between the two treatment groups in the proportion of patients initiating and adhering to optimal medical treatment (event prevention, antianginal therapy), assessed at 1 year after randomization.

6.4.3 Statistical Hypothesis, Model and Method of Analysis

- A. The statistical null hypothesis is that there is no difference in basic lifestyle measures from baseline to 3 months, and 1 year, respectively, after randomization between the two treatment groups.
- B. The statistical null hypothesis is that there is no difference in the proportion of patients initiating and adhering to optimal medical treatment (event prevention, antianginal therapy), assessed at 1 year after randomization between the two treatment groups.

Comparisons between treatment group will be made with Mann-Whitney U test.

6.5. Safety

6.5.1 Objectives

- A. To investigate the proportion of each of the individual components of major adverse cardiac events (all-cause death, myocardial infarction, unstable angina pectoris, heart failure, ischaemic stroke, major complication of cardiovascular procedures or diagnostic testing within 72 hours) in the two treatment groups at 1 year after randomization.
- B. To investigate the difference between the two treatment groups in the cumulative contrast dose, assessed at 1 year after randomization.
- C. To investigate the difference between the two treatment groups in the cumulative radiation dose, assessed at 1 year after randomization.
- D. To investigate the difference between the two treatment groups in the proportion of bleedings requiring hospitalization, assessed at 1 year after randomization.
- E. To assess the adverse events related to the CADScor®System in the intervention group.

6.5.2 Endpoints

- A. Difference between the two treatment groups in the proportion of each of the individual components of major adverse cardiac events (all-cause death, myocardial infarction, unstable angina pectoris, heart failure, ischaemic stroke, major complication of cardiovascular procedures or diagnostic testing within 72 hours), assessed at 1 year after randomization.
- B. Difference between the two treatment groups in the cumulative contrast dose, assessed at 1 year after randomization.
- C. Difference between the two treatment groups in the cumulative radiation dose, assessed at 1 year after randomization.
- D. Difference between the two treatment groups in the proportion of bleedings requiring hospitalization, assessed at 1 year after randomization.
- E. Adverse events related to the CADScor®System in the intervention group.

6.5.3 Statistical Hypothesis, Model and Method of Analysis

- A. The statistical null hypothesis is that there is no difference in the proportion of each of the individual components of major adverse cardiac events (all-cause death, myocardial infarction, unstable angina pectoris, heart failure, ischaemic stroke, major complication of cardiovascular procedures or diagnostic testing within 72 hours) between the two treatment groups, assessed at 1 year after randomization.
- B. The statistical null hypothesis is that there is no difference in the cumulative contrast dose, assessed at 1 year after randomization between the two treatment groups. Comparisons between treatment group will be made with Mann-Whitney U test.
- C. The statistical null hypothesis is that there is no difference in the cumulative radiation dose, assessed at 1 year after randomization between the two treatment groups.
- D. The statistical null hypothesis is that there is no difference in the proportion of bleedings requiring hospitalization, assessed at 1 year after randomization between the two treatment groups.
- E. The statistical null hypothesis is that there is no difference in adverse events related to the CADScor®System between the two treatment arms.

Comparisons between treatment group will be made with Mann-Whitney U test. Comparisons of categorical data will be done using Fisher's exact test.

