4.1. Primary endpoint

Difference between the two treatment groups in cumulative number of non-invasive and invasive diagnostic procedures, assessed at 1 year after randomization. NITs include exercise ECG, CCTA, Rb-PET CT, MPI, CMRI and stress echocardiography. Invasive procedures include invasive coronary angiographies (ICA) only.

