A reduction of 15% or more in the primary endpoint is regarded as clinically significant. Assuming an alpha significance level of 0.05, a statistical power of 80% and an expected number of NIT/ICA of 0.94 per patient in the standard care group, a sample size of 314 patients in each arm is needed to ascertain superiority of the intervention, in this case an absolute reduction in the primary endpoint of 0.17 NIT/ICA per patient, i.e. number of NIT/ICA.

The expected number of NIT/ICA of 0.94 in the control group and 0.77 in the intervention group is based on the following sequence of assumptions:

- No. of first NITs: n=760 in the control group (all patients with DF-score 15-85%) and n= 610 in the intervention group (all patients with a CAD-score not ruling out CAD + 20% of patients with a CAD-score ruling out CAD).
- No. of second NITs: 10% of first NIT; n=76 in the control group and n=61 in the intervention group.
- No. of ICAs: 10% of total population; n=100 in each group.

Note: the patient pathway is expected to change only slightly due to the updated ESC 2019 guidelines (Knuuti *et al.* 2019). Current data indicates that the number of patients in each arm will increase to 521 for the primary endpoint; which stays within the total number of 2000 patients as described below.

Given the abovementioned assumptions, the mean number of investigations (NITs and ICAs combined) per patient will be 0.94 in group 1 and 0.77 in group 2. A sample size of 314 patients in each arm will then provide 80% power for testing superiority in terms of number of diagnostic procedures for the group with CAD-score stratification compared to the group with DF-score only stratification, at an alpha significance level of 0.05.

The study allows for some degree of cross-overs where patients with PTP or CAD-score ruling out CAD instead are crossed-over to a NIT. The power calculation simulates a worst-case scenario where the two

groups (control and intervention group) have the lowest expected difference in number of diagnostic procedures; 0% of patients with low PTP ruling out CAD (Diamond-Forrester(DF) <15 %) crossed-over to NIT in the control and 20% of patients with a CAD-score ruling out CAD in the intervention group crossed-over to NIT.

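### Cumulative contrast and radiation dose are compared by a rank test alone, which mostly reflects who received any dose and gives no estimate of the dose difference

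*SAP*

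**What the plan says.** SAP 6.5.2 defines safety endpoint C as "Difference between the two treatment groups in the cumulative radiation dose, assessed at 1 year after randomization", and endpoint B in the same way for contrast. Section 6.5.3 B names Mann-Whitney U for contrast, with the null given as "no difference in the cumulative contrast dose, assessed at 1 year after randomization between the two treatment groups. Comparisons between treatment group will be made". Item C names no test of its own, so radiation dose falls under the section's last lines: "Comparisons between treatment group will be made with Mann-Whitney U test. Comparisons of categorical data will be done using Fisher's exact test".

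For B and C the section names no mean difference, ratio or confidence interval, and does not say how patients without a procedure enter. The mean-or-median rule in section 3 concerns baseline data. Section 1 says that all analyses are stratified by site and pre-test probability (PTP), but no stratified form of the rank test is named in 6.5.3.

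Two other places bear on how many patients have zero dose. Section 4.2 plans, for 1000 patients per group, "No. of first NITs: n=760 in the control group (all patients with DF-score 15-85%) and n= 610 in the intervention group", with "No. of second NITs: 10% of first NIT; n=76 in the control group and n=61 in the intervention group" and "No. of ICAs: 10% of total population; n=100 in each group". Section 4.1 lists the procedures: "NITs include exercise ECG, CCTA, Rb-PET CT, MPI, CMRI and stress echocardiography. Invasive procedures include invasive coronary angiographies (ICA) only".

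**The concern.** Cumulative dose is an amount that adds up over procedures, and the endpoint is worded as a difference between groups in that amount. Many patients will have a total of exactly zero, and the strategy under test changes that share by design. With many tied zeros, a rank test responds mainly to the share of patients with any dose and less to how much the exposed patients received.

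Two things are at stake. First, the analysis as written produces a p-value but no figure for dose saved or added; if fewer than half of the patients in each arm have any dose, that p-value stands beside two medians of zero. Second, a safety endpoint on dose should be able to show a shift to fewer but heavier exposures. In that situation the rank test can point to a lower dose when the mean is not lower.

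**Working it through.** **1. The plan's own figures.** From section 4.2, per 1000 patients:
- Control: (760 + 76 + 100)/1000 = 0.936, stated as 0.94.
- Intervention: (610 + 61 + 100)/1000 = 0.771, stated as 0.77.

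Both are reproduced. The shares without a first NIT are 1 - 0.76 = 24% and 1 - 0.61 = 39%. Exercise ECG, stress echocardiography and CMRI use no ionising radiation, so more patients than this may have zero radiation dose.

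**2. What drives the rank test.** Let p be the share with any dose and q = 1 - p. The fraction of the rank variance that comes from the zero/non-zero split is (pq/4) / ((1 - q³)/12) = 3pq/(1 - q³).
- p = 0.76: 0.5472/0.9862 = 55%
- p = 0.685 (average of 0.76 and 0.61): 67%
- p = 0.50: 0.75/0.875 = 86%
- p = 0.25: 0.5625/0.5781 = 97%

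**3. Mean dose under the plan.** The SAP gives no doses, so these are assumptions: an NIT that carries dose gives 1 unit, a share c of NITs carry dose, and an ICA gives r units. With intervention ICA rate p_ICA:
- Control mean = 0.836c + 0.1r
- Intervention mean = 0.671c + p_ICA·r

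With p_ICA = 0.1 as planned, the intervention mean is lower by 0.165c whatever r is, so means and ranks point the same way.

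**4. Departure from the plan.** The means are equal when p_ICA = 0.1 + 0.165c/r. Trials of 1000 per arm were simulated at that rate, with ICAs only in tested patients, log-normal dose spread (log SD 0.3) and two-sided 5% tests. The table gives how often Mann-Whitney U declares the intervention dose lower although the true means are equal. Ranges are over repeat runs; with 400 trials the standard error is at most √(0.25/400) = 2.5 points.

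| r | ICA rate, c = 1 | Declared lower, c = 1 | ICA rate, c = 0.5 | Declared lower, c = 0.5 |
|---|---|---|---|---|
| 1 | 0.265 | 17-25% | 0.1825 | 12-18% |
| 2 | 0.1825 | 82-84% | 0.141 | 32-33% |
| 3 | 0.155 | 95-96% | 0.1275 | 55-56% |
| 5 | 0.133 | 99% | 0.1165 | 67-73% |

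A Welch comparison of means does so in 2-5%, near the nominal 2.5%. At c = 0.5 both medians are 0 in nearly every trial. With the intervention mean truly 10% higher and r = 3, Mann-Whitney U still declares it lower in 73-76% of trials (22% at c = 0.5). The r = 1, c = 1 cell depends on spread: log SD 0.6 gives 61%.

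**5. A different model.** Here dose is zero or log-normal (log SD 0.5), the exposed shares differ and the means are equal. Mann-Whitney U declares a lower dose in 32% of trials at 76% vs 61% exposed, 57% at 50% vs 40%, 53% at 25% vs 20%, and 17% at 25% vs 22.3%. The comparison of means gives 1.9-2.9%.

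**The case against.** **The SAP never says mean.** It speaks of a difference in cumulative dose, and Mann-Whitney U is a valid test of identical distributions. A reader might infer that the test is invalid or contradicts the SAP; neither follows. What remains is that the endpoint is a difference in dose and the named method does not estimate one.

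**The wrong direction needs an unplanned scenario.** A reader might infer that the plan, followed as written, will mislead. Section 4.2 does not support that: with 100 ICAs per group the direction is right. At c = 1 the equal-mean settings need 133 to 265 intervention ICAs per 1000, which is 33% to 165% more than planned, and smaller increases leave mean dose truly lower. This stands, and the simulated percentages are conditional on it.

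**Ranks do not ignore dose.** With 70% exposed in both arms and a 10% higher dose in one, Mann-Whitney U detects the difference in 53% of trials against 63% for the means. A claim that the test sees only who was tested goes too far.

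**The counts are from the protocol 3.0 pathway.** The SAP notes that the number needed rises from 314 to 521 per arm. If only the effect shrank, the gap in first NITs falls by a factor √(314/521) = 0.78, from 15 to about 12 points. With 76% vs 64.5% tested (an assumed gap), the figures at r = 1, 2, 3 and 5 become 9%, 62%, 82% and 89%, or 10%, 24%, 32% and 44% at c = 0.5. The problem is smaller but remains.

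**More ICAs would be seen elsewhere.** Section 6.2.2 C and D compare ICAs and negative ICAs. In the scenarios above, Fisher's test on patients with an ICA shows the excess in 100%, 100%, 96% and 63% of trials at c = 1, and in 100%, 76%, 49% and 20% at c = 0.5. This is a partial safeguard, and it gives no dose.

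**Conclusion.** The point holds as a gap in what 6.5.3 B and C will deliver. The named test gives no dose difference, and 55% or more of its rank variance comes from the split between any dose and none when 76% or fewer of the patients have a dose. If the intervention arm had more ICAs or heavier exposure per patient than section 4.2 assumes, the test could indicate a lower dose at equal or higher mean dose: about 17-99% of simulated trials at equal means if all NITs carry dose, and about 12-67% if half do (up to 73% in a repeat run). These figures rest on assumed dose ratios of 1 to 5, an assumed spread and the protocol 3.0 counts. One model also stands in for both contrast and radiation, although the procedures that contribute to each differ.

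The SAP does not support a claim that the direction will be wrong under its own assumptions, nor that Mann-Whitney U should be reduced to a supportive role; the latter is a trade-off in power. Only non-key secondary safety endpoints are affected. The primary and MACE conclusions do not depend on this.

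**What to change.** In 6.5.3 B and C, add:
- the difference in mean cumulative dose per randomised patient, counting patients without a procedure as 0, with a 95% bootstrap interval resampled within arm and the randomisation strata (site and PTP);
- beside it, the proportion with any dose and the dose among those exposed, by arm.

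Keep Mann-Whitney U as the rank test, and state that any wording that cumulative dose is lower or higher rests on the mean difference and its interval.

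The cost is a few lines of SAP text and some programming; the dose data are already needed for these endpoints. The real downside is sensitivity when only the share tested differs. With ICAs equal and r = 3, the mean comparison is significant in about 85% of simulated trials against 100% for the rank test, or about 35% against 87% if half of NITs carry dose. At r = 5 with all NITs carrying dose it is about 56% against 100%. This is the reason to retain both.

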6.5.1 Objectives	13
6.5.2 Endpoints.....	14
6.5.3 Statistical Hypothesis, Model and Method of Analysis	14
6.6. Quality of Life	14

6.6.1 Objective.....	14
6.6.2 Endpoint	15
6.6.3 Statistical Hypothesis, Model and Method of Analysis	15
7. Sensitivity Analysis.....	15
8. Missing Data	15
9. References	15

1. Background and Study Design

The FILTER-SCAD trial is a randomized, controlled, multicentre, superiority trial with two parallel groups investigating the use of the acoustic measured risk score (CAD-score) for obstructive coronary artery disease (CAD) for ruling out CAD as compared to current standard diagnostic strategy in patients with symptoms suggestive of CAD.

Approximately 2000 patients with symptoms suggestive of CAD referred for outpatient assessment are expected to be enrolled at 5 study sites in Denmark and 1 in Sweden. The subjects will be randomized 1:1 to either 1) standard diagnostic strategy i.e. pre-test probability (PTP) stratification followed by non-invasive test (NIT), if indicated (control group), or (2) PTP plus CAD-score stratification followed by NIT, if indicated (intervention group). Randomization is stratified according to study site and PTP. Given the stratified design, all analyzes are carried out stratified by site and PTP.

2. Analysis Datasets

All patients from whom written informed consent are obtained will be included in the **full analysis set (FAS)**. Subjects will be analysed according to the allocated randomization group in accordance with the intention-to-treat principles.

The **per protocol set (PPS)** will include the subjects from the FAS who did *not* have one of the following major protocol violations:

- inclusion criteria not met
- exclusion criteria met
- no PTP calculation
- no CAD-score measurement (intervention group only).

Patients who did not receive the randomly allocated CAD-score measurement will be included and analysed in the control group (per protocol analysis).

The **screened analysis set (SAS)** will include all screened patients who receive a subject number.

3. Demographics and Baseline Characteristics

Continuous variables will be presented as mean and standard deviation for variables following a normal distribution or as median with interquartile range if showing a skewed distribution. Categorical variables will be presented as frequencies and percentages. Categorical data will be compared using Fisher's exact

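### SAP 6.5.3 E sets a between-arm test for device-related adverse events, although 6.5.1 E and 6.5.2 E confine them to the intervention group and controls are not measured with the device

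*SAP*

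**What the plan says.** Section 6.5 of the SAP treats item E in three places.

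- Objective, 6.5.1 E: "To assess the adverse events related to the CADScor®System in the intervention group".
- Endpoint, 6.5.2 E: "Adverse events related to the CADScor®System in the intervention group". Endpoints A to D in the same list are each worded as a difference between the groups; E is not.
- Hypothesis, 6.5.3 E: "The statistical null hypothesis is that there is no difference in adverse events related to the CADScor®System between the two treatment arms".

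Section 6.5.3 closes with two sentences covering the whole list: "Comparisons between treatment group will be made with Mann-Whitney U test. Comparisons of categorical data will be done using" Fisher's exact test. Neither sets E aside.

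Exposure to the device follows from sections 1 and 2. The control strategy is "standard diagnostic strategy i.e. pre-test probability (PTP) stratification followed by non-invasive test (NIT), if indicated (control group"). The intervention strategy is "PTP plus CAD-score stratification followed by NIT, if indicated (intervention group"). Among the major protocol violations, section 2 lists "no CAD-score measurement (intervention group only"), so a CAD-score is expected in that arm alone.

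**The concern.** The objective and endpoint ask a one-sample question: what adverse events does the device cause in the patients measured with it? The hypothesis asks a two-sample question, with a comparison arm that is not exposed to the device. The sections cannot all be followed, and the one that fixes the analysis does not answer the stated objective.

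This matters for how the result is read. A non-significant p-value could be taken as reassurance about the device when it says only that few events were seen. A significant one would say that several device-related events occurred, but not how often they occur or how precisely that is known. Item E is the only endpoint in the SAP devoted to the safety of the device itself, and no rate or interval is specified for it.

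**Working it through.** The SAP gives no sample size, event rate or power for item E, so there is no planned figure to reproduce. The calculation below only shows how the named tests behave.

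**Inputs**

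- Patients per arm: 1000. Section 1 says "Approximately 2000 patients with symptoms suggestive of CAD referred for outpatient assessment are expected to be enrolled", with 1:1 allocation; 2000 / 2 = 1000.
- Control events: 0, from the design in sections 1 and 2.
- Significance level: two-sided 0.05. This is an assumption. The SAP states 0.05 in the sample-size text of 4.2 and 5.2, not for E.
- Device-event rate: not given, so a range is used.

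**Step 1: Fisher's exact test, x of 1000 against 0 of 1000.** With zero controls the two-sided p-value is

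p = 2 × C(1000, x) / C(2000, x) for x ≥ 1,

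which depends on x alone.

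- x = 5: 2 × (1000·999·998·997·996) / (2000·1999·1998·1997·1996) = 2 × 0.0311 = 0.062.
- x = 6: multiply by 995/1995, giving 0.031.

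**Step 2: Mann-Whitney on the same 0/1 data**, with tie and continuity corrections. At x = 4, U exceeds its null mean by 4 × 1000 / 2 = 2000, and its tie-corrected standard deviation is 999.2. So z = (2000 − 0.5) / 999.2 = 2.00 and p = 0.045.

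| Intervention events (controls 0) | Fisher p | Mann-Whitney p |
|---|---|---|
| 1 | 1.00 | 0.318 |
| 2 | 0.50 | 0.157 |
| 3 | 0.25 | 0.083 |
| 4 | 0.125 | 0.045 |
| 5 | 0.062 | 0.025 |
| 6 | 0.031 | 0.014 |

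The two tests named in 6.5.3 fall on opposite sides of 0.05 at 4 and 5 events. Both thresholds are the same at 957 per arm (1914 / 2, from the sample size in 5.2).

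**Step 3: chance that Fisher rejects.** This is P(X ≥ 6) with X binomial(1000, r), for assumed device-event rates r.

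| Assumed rate r | P(X ≥ 6) |
|---|---|
| 0.1% | 0.0006 |
| 0.2% | 0.0165 |
| 0.3% | 0.084 |
| 0.5% | 0.384 |
| 1.0% | 0.934 |

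The null of equal risk is false in every row, yet it would rarely be rejected in the first three.

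**Step 4: what a one-sample summary gives.** Clopper-Pearson 95% intervals:

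- 5 of 1000: 0.5%, interval 0.16% to 1.16%. This is the result that Fisher would call non-significant.
- 0 of 1000: upper limit 1 − 0.025^(1/1000) = 0.37%.

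The interval is informative at any count, including zero, and addresses 6.5.1 E directly.

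**The case against.** The strongest reply is that this is a drafting slip of little consequence. Section 6.5.3 repeats one no-difference formula from A to E, and E is the last item in a list under the other secondary objectives. Endpoint E already consists of the events in the intervention group, and any Fisher test needs that count, so the superfluous null adds a p-value without removing the endpoint. Misreading a non-significant result is a possibility, not something the SAP instructs. For a yes/no outcome Fisher is the natural choice, so the disagreement with Mann-Whitney may not arise. These points stand, and they limit the weight of the finding. They do not remove it: reporting E descriptively would depart from the text of 6.5.3, and the SAP does not say whether E is a count of events or a proportion of patients.

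A reader might also infer more than the document supports:

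- **That the null is known to be false.** It is false only if the device carries a non-zero risk, and the SAP gives no such risk. At zero risk the null is true, and the comparison still has no informative control.
- **That a significant result shows merely that the device was used.** Use alone cannot produce significance; under the assumptions above, Fisher needs at least 6 device-related events.
- **That control events are zero by definition.** They are zero by design. Nothing in section 2 rules out an off-protocol measurement in a control, although endpoint E would not count it.
- **That up to 5 events would always be non-significant.** This holds for Fisher at an assumed two-sided 0.05, not for Mann-Whitney.

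**Conclusion.** Wrong as written, and minor. The hypothesis in 6.5.3 E contradicts the objective and endpoint it is meant to serve, and the tests attached to it yield a p-value determined by the intervention-arm event count alone. The contradiction rests only on the text of the SAP. The figures are an illustration that assumes about 1000 per arm, no control exposure and a two-sided 0.05 level; they do not measure a known error in the trial, because no device-event rate is given. No sample size, hypothesis or conclusion for the primary or key secondary endpoint depends on this item.

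**What to change.** Three edits to 6.5.3:

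1. Delete the between-arm null for item E.
2. State in the closing test sentences that they do not apply to E.
3. Specify for E the number and percentage of patients with at least one device-related adverse event, among those actually measured with the device, with a Clopper-Pearson 95% interval.

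Deleting the null and exempting E are what the contradiction requires. The exact interval and the measured-patients denominator are a recommended way to fill the gap. That denominator suits the objective, since a patient allocated to the intervention arm but not measured was not exposed to the device.

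The cost is a sentence or two in the SAP. No new data are needed, and no other analysis changes.
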